### 10.2 Sample Size Considerations

With 33 patients in each olezarsen treatment group and 22 in the pooled placebo group, there would be an approximately 80% power to detect a 60% difference between each olezarsen treatment group and pooled placebo group at an alpha level of 0.05 (two-sided), assuming 60% reduction in the olezarsen treatment patients, no change in the placebo patients, and a common SD of approximately 73%. It is estimated that dropout rate is approximately 20%.

Approximately 152 patients will be enrolled in this trial to account for potential early dropouts and to facilitate general safety evaluations.

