The Markov Chain Monte Carlo (MCMC) method will be used under the multivariate normality assumption to impute the missing values by treatment group. The variable list for imputations will include the baseline value, as well as all available post-baseline value. To conform to the multivariate normality assumption, baseline and post-baseline fasting TG will be natural log-transformed before the imputation process, the data will be back transformed to create the imputed data set after the imputation. The SAS procedure PROC MI will be used to create 1000 imputed datasets. The first 100 imputed datasets with imputed values within the analytical measuring range will be chosen from 1000 imputed datasets for the analysis.

Default EM algorithm will be used to derive a set of initial parameter estimates for MCMC method. A non-informative prior (Jeffreys' prior) will be used to derive the posterior distribution of the parameters.

The following pseudo SAS code and seed (2438291) will be used to perform the multiple imputation:

Step 1, using PROC MI to generate 1000 imputations:

```

/*****
/* Note:
/* baseline = baseline fasting TG
/* impute = the iteration number in the multiple imputation
/* trtpn = Treatment group: 0=Placebo, 1= olezarsen 50 mg, 2 = olezarsen 80 mg*/
*****/

proc mi data = TG seed = 2438291 nimpute = 1000 out=TGIM;

    transform log(baseline) log(week5) log(week9) log(week13) log(week17)
    log(week21) log(month6) log(week29) log(week37) log(week45) log(month12);

    mcmc;

    var baseline week5 week9 week13 week17 week21 month6 week29 week37 week45
    month12;
    by trtpn;

run;

```

Step 2, extract placebo data, fit a GLM model using log transformed data for each imputation and get parameter estimates:

```

proc glm data=pla_mar;
    by paramcd imputation_;
    model AVAL_log=base_log avisitn_interval/solution;

run;

```

Step 3, for patients in the active arm, remove the imputed data post last "observed value", apply the parameter estimates calculated from step 2 to active treatment arms and back transformed the data to create the 1000 imputation datasets.

Step 4: Set the dataset from step 3 and the subset of placebo dataset (the dataset used in step 2) together then choose the first 100 imputation dataset with imputed values within the analytical measuring range.

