**The attributes and description of the estimands are provided in the tables below:**

Treatments	
 
• olezarsen 80 mg
 
• placebo
 

Participant Population	Patients with hypertriglyceridemia and atherosclerotic cardiovascular disease (ASCVD) (established, or at increased risk for), or with severe hypertriglyceridemia (SHTG) as defined by protocol eligibility criteria
Variable	Percent change from Baseline to Month 6 (average of Weeks 25 and 27) in fasting TG
Intercurrent events (ICEs) and strategies	
 
• Discontinuation of study treatment prior to Week 25 Treatment policy strategy
 
• Disallowed concomitant therapy/procedure prior to Week 25 Treatment policy strategy
 

Population-level summary	Difference in means of percent change between olezarsen 80 mg and placebo in the FAS
Description of estimand	The difference in means of percent change from Baseline to the Month 6 in fasting TG between olezarsen 80 mg and placebo (regardless of early treatment discontinuation, use of additional medication, or change in background or concomitant treatments) in patients with hypertriglyceridemia and ASCVD (established, or at increased risk for), or with SHTG

For each of the 100 imputed datasets obtained from Section 4.9.1.4, the percent change from Baseline to Month 6 in fasting TG will be compared between olezarsen treatment groups and placebo using an analysis of covariance (ANCOVA) model that assumes unequal variance with percent change from Baseline to Month 6 in fasting TG as the dependent variable, treatment group (olezarsen 80 mg, olezarsen 50 mg, or Placebo) as factor, and natural log-transformed baseline fasting TG as a covariate.

The pseudo SAS code of ANCOVA:

```

/*****
/* Note:
/* baseline = baseline TG
/* impute = the iteration number in the multiple imputation
/* trtpn = Treatment group: 0=Placebo, 1= olezarsen 50 mg, 2 = olezarsen 80 mg*/
/* pchg = percent change TG from baseline to Month 6
*****/

data TG; set TG;
    logbase = log(baseline); /* log transformed baseline*/
proc mixed data = TG;
    by impute;
    class trtpn;
model pchg = trtpn logbase/ ddfm=satterth;
    lsmeans trtpn/e diff cl;
    estimate 'olezarsen 50 mg vs Placebo' trtpn -1 1 0;
    estimate 'olezarsen 80 mg vs Placebo' trtpn -1 0 1;
run;

```

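### If the jump-to-reference fallback is used, its coded steps impute olezarsen discontinuers at a fitted log-scale mean with no residual draw, which shifts the TG estimate modestly toward olezarsen and narrows its interval

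*Combined protocol and SAP*

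**What the plan says.** SAP Section 4.9.1.4 imputes missing Month 6 and Month 12 fasting TG from retrieved dropouts if there are enough of them. Otherwise it falls back on a washout (J2R) approach. The prose says that olezarsen discontinuers then have their missing values multiply imputed from baseline TG and the placebo imputation model. SAP Section 4.13 confirms that this replaces the protocol's method for the primary analysis. What counts as a sufficient number of retrieved dropouts is not defined.

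The code that follows has four steps:

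- Step 1 runs MCMC imputation by arm.
- Step 2 fits PROC GLM to log TG in each completed placebo dataset, with the statement "model AVAL_log=base_log avisitn_interval/solution".
- Step 3 deletes the olezarsen imputations after the last observed value and is told to "apply the parameter estimates calculated from step 2 to active treatment arms and back transformed the data to create the 1000 imputation datasets".
- Step 4 applies a filter: "The first 100 imputed datasets with imputed values within the analytical measuring range will be chosen from 1000 imputed datasets for the analysis".

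The end of Section 4.9.1.4 carries Steps 2 to 4 over to the other lipids. The summary measure in the estimand table of SAP Section 4.9.2.1 is "Difference in means of percent change between olezarsen 80 mg and placebo in the FAS".

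**The concern.** Three things do not fit together.

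- **Prose and code differ.** The prose promises multiple imputation. In the olezarsen arm the code produces a fitted value. The coefficients change between imputations only because some placebo values were themselves imputed. If no placebo value is missing, the coefficients are the same in all 1000 datasets, and the imputed olezarsen values do not vary at all.
- **The scale is wrong for the estimand.** Exponentiating a fitted log mean gives a conditional median. For right-skewed TG the median lies below the mean, and the estimand is a difference in means.
- **The arms are treated differently.** Imputed placebo values keep their MCMC draws, including the upper tail. Imputed olezarsen values do not.

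At stake are the size of the headline TG effect and the width of its interval, in a step meant to be conservative. The same imputed data feed the Month 12 analysis, sensitivity analyses 3, 4 and 6, and the responder analyses.

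**Working it through.** **Inputs.** Protocol Section 10.2 gives the planning figures: "With 33 patients in each olezarsen treatment group and 22 in the pooled placebo group", "approximately 80% power to detect a 60% difference between each olezarsen treatment group and pooled placebo group", "no change in the placebo patients", a common SD of about 73%, two-sided alpha 0.05 and about 20% dropout. Randomizing 152 patients 1:1 to cohorts and 3:1 within each gives 57 / 57 / 38 (pooled placebo). Two quantities are not in the documents and are assumed as ranges: the residual log-SD, s, and the share of olezarsen patients with Month 6 TG missing after discontinuation.

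**The plan's own figure.** SE = 73 × √(1/33 + 1/22) = 20.09, and 60/20.09 = 2.99. Power is Φ(2.99 − 1.96) ≈ 84.8% (normal) or 83.4% (noncentral t), against the stated 80% or so. The stated size is slightly conservative, and nothing below depends on it.

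**Shortfall per imputed patient.** Let the placebo ratio of Month 6 to baseline TG be log-normal with mean 1 (zero mean change). Its conditional median is exp(−s²/2). The plug-in is therefore too low by 100 × (1 − exp(−s²/2)) percentage points. An SD of 73% with zero mean change implies exp(s²) − 1 = 0.73², so s = √ln(1.5329) = 0.654.

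| s | Shortfall per imputed patient | Arm mean, 10% missing | Arm mean, 20% missing |
|---|---|---|---|
| 0.35 | 5.9 | 0.6 | 1.2 |
| 0.50 | 11.8 | 1.2 | 2.4 |
| 0.654 | 19.2 | 1.9 | 3.8 |

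**Simulation.** 57/57/38 patients, 4000 trials per setting, 50 imputations, ANCOVA on percent change with log baseline, Rubin's rules. Steps 2 and 3 as coded were compared with J2R that draws both parameters and a residual. A single Month 6 value was used in place of the pooled-visit GLM. Entries are estimate (mean pooled SE).

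| s | Missing | Effect on drug | With draws | As coded | Shift | SE smaller by |
|---|---|---|---|---|---|---|
| 0.35 | 20% | 60% | −48.1 (8.07) | −49.4 (6.62) | 1.3 | 18% |
| 0.50 | 10% | 0 | 0.02 (12.02) | −1.34 (11.20) | 1.4 | 7% |
| 0.50 | 10% | 60% | −53.90 (9.20) | −55.25 (7.83) | 1.4 | 15% |
| 0.50 | 20% | 0 | 0.25 (12.96) | −2.49 (11.33) | 2.7 | 13% |
| 0.50 | 20% | 60% | −47.79 (11.15) | −50.55 (8.76) | 2.8 | 21% |
| 0.654 | 10% | 0 | −0.20 (16.70) | −2.49 (15.44) | 2.3 | 8% |
| 0.654 | 10% | 60% | −53.77 (12.58) | −56.08 (10.47) | 2.3 | 17% |
| 0.654 | 20% | 0 | −0.23 (18.33) | −4.84 (15.87) | 4.6 | 13% |
| 0.654 | 20% | 60% | −47.90 (15.35) | −52.58 (11.76) | 4.7 | 23% |

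At s = 0.35 with 10% missing the shift was about 0.7. Over all settings the SE was 6% to 13% smaller with a null drug and 13% to 23% smaller with a 60% effect. A second, smaller simulation (1500 trials, 30 imputations, simple mean difference) gave shifts of 0.65 to 2.27 at 10% missing and 1.33 to 4.65 at 20%. The simulated shift is a little larger than the formula. Drawing parameters estimated from a small placebo arm slightly raises the mean of the exponentiated values, and the plug-in omits that as well.

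**Type I error.** With a null drug, two-sided rejection was 3.4% to 4.2% as coded and 1.2% to 2.8% with draws.

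**The case against.** **It is a fallback, and 20% is not the Month 6 missing rate.** This stands as a limit. The step applies only if retrieved dropouts are too few, and only to olezarsen discontinuers with no Month 6 TG. Protocol Section 8.7.1 urges discontinuers to attend Weeks 25 and 27, and under SAP Section 4.2.2 either value is enough. The planned 20% is overall dropout, so those rows are an upper case. The fallback is still not remote: 20% of 57 is about 11 dropouts per olezarsen arm, retrieved ones are a subset, and the by-arm model lists 11 variables.

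**It is only pseudo-code.** The SAP says the code will be used and extends the steps to the other lipids. If a draw is intended, the text needs to say so, and a correction is needed either way.

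**A reader might infer that a null drug would be declared effective too often.** The simulation does not support this, because rejection stayed below 5%. J2R with draws under Rubin's rules is itself conservative, so part of the SE gap reflects that. With a 60% effect and s of 0.50 or 0.654, coverage as coded was about 94% at 20% missing and 90% to 91% at 10%. At 10% missing the same ANCOVA on complete data covered only 88% to 89%, so that shortfall cannot be put down to the plug-in.

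**A reader might infer that the responder endpoints gain the same advantage.** They need not. Entry requires TG of at least 150 mg/dL, so a fitted value near baseline usually stays above 150. In a simulation with an assumed baseline median of 260 mg/dL, 14% to 26% of olezarsen dropouts counted as below 150 as coded, against 20% to 36% with draws. For HDL-C and apoA-1 a downward bias also works against olezarsen if a rise is the hoped-for result.

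**Existing sensitivity analyses would show the problem.** In part. The completer analysis uses no imputed Month 6 value, and the log-ratio ANCOVA (analysis 6) avoids the retransformation bias, though not the missing variance. The Wilcoxon and tipping-point analyses start from the same imputed values. None of these corrects the primary estimate.

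**Conclusion.** The point holds for the fallback as coded and should be fixed, but it does not decide the trial. Steps 2 and 3 are not the multiple imputation that the prose describes. They move the TG estimate toward olezarsen by about 0.7 to 2.3 points at 10% missing and 1.3 to 4.7 at 20%, and they shrink the pooled SE by 6% to 23% relative to J2R with draws. These sizes rest on an assumed residual log-SD of 0.35 to 0.654 and an assumed Month 6 missing rate. The value 0.654 treats the plan's common SD of percent change as if it were a residual SD given baseline, so it is illustrative. Against a planned 60-point effect, a shift of at most about 5 points would not by itself reverse the primary conclusion.

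Two stronger readings are not supported. The first is that imputation uncertainty vanishes: in the simulations the between-imputation SD was about 25% to 30% smaller, and it is zero only when no placebo value is missing. The second is that the Step 4 filter leaves too few datasets or causes a known bias. Selecting whole datasets on their imputed values is poor practice, but its effect cannot be quantified because the assay range is not given.

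**What to change.** In Step 3, draw the placebo regression parameters (coefficients and residual variance) from their posterior for each imputation, add a residual draw on the log scale, and only then exponentiate. Step 2 pools visits, so where several visits are imputed for one patient the residuals should be drawn jointly. Alternatively, use PROC MI with an MNAR MODEL statement and placebo as the reference, run without the by-arm split so that placebo is available to the olezarsen arms. Make the same change for the other lipids, and bring the prose and the code of Section 4.9.1.4 into agreement.

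As a secondary change, replace the Step 4 rule with handling of individual out-of-range values, for example bounding the draw or setting it to the assay limit, and analyse all imputations.

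The cost is a few lines of SAS and some SAP wording. If the fallback is used, expect a slightly less favourable TG estimate and a wider interval.

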**Multiple imputation for missing fasting lipids (excluding TG) at baseline and Month 6/Month 12:**

For other lipid data (apoC-III, VLDL-C, remnant cholesterol, non-HDL-C, HDL-C, TC, apoB, LDL-C, and apoA-1), a two-stage multiple imputation approach will be utilized to impute the missing values at baseline, Months 6 and Month 12 if baseline is missing for at least one randomized patient for given lipid parameter.

First, the missing baseline fasting lipid value will be multiply imputed based on the observed baseline assessments from other patients. The MCMC method ([Schafer 1997](#); [Schafer 1999](#)) will be used to impute the missing values. The imputation model will include baseline fasting lipid value and baseline stratification factor (i.e., baseline fasting TG  $\geq$  500 mg/dL (yes/no). The baseline lipid value will be natural log-transformed before the imputation process, the data will be back transformed to create the imputed data set after the imputation. The SAS procedure PROC MI will be used to create 1000 imputed datasets.

The following pseudo SAS code and seed (2438291) will be used to perform the multiple imputation for missing lipid data at baseline:

```
/* **** */
/* Note: */
/* baseline = baseline fasting lipid value */
/* stratt = Baseline TG >= 500 mg/dL (5.65 mmol/L) Yes/No */
/* **** */
proc mi data = adeff seed = 2438291 nimpute = 1000 out= adeff2;
    transform log(baseline);
    mcmc;
    var stratt baseline;
run;
```

The imputed baseline values will be merged with the observed post baseline data and used for the second stage of imputation.

In the second stage of imputation, the missing lipid value at Months 6 and/or 12 will be imputed using similar method described above for missing fasting TG at month 6 and/or month 12, with an imputation model that contains the following variables: baseline fasting lipid value, fasting lipid value at each post-baseline visits and baseline stratification factor. The multiple imputation will be stratified by treatment group ([Schafer 1997](#); [Schafer 1999](#)).

The following pseudo SAS code and seed (2438291) will be used for the second stage of imputation:

```

/*****
/* Note:
/* baseline = baseline lipid parameter
/* trtpn = treatment group: 0=placebo, 1=olezarsen 50 mg, 2=olezarsen 80 mg
/* _imputation_ = the iteration number in the stage 1 imputation
/* stratt = baseline TG >= 500 mg/dL (5.65 mmol/L) Yes/No
*****/
proc sort data=adeff2;
    by _imputation_;
run;
proc mi data=adeff2 (where=(trtpn=0)) seed=2438291 nimpute=1 out=imputed;
/*repeat the procedure for each treatment group by replacing trtpn category in the
where option*/
    transform log(baseline) log(week5) log(week9) log(week13) log(week17) log(week21)
log(month6) log(week29) log(week37) log(week45) log(month12);
    mcmc;
    var baseline stratt week5 week9 week13 week17 week21 month6 week29 week37 week45
month12;
    by _imputation_;
run;

```

For lipid parameters with no missing data at baseline, the baseline imputation will not be performed. The second stage of imputation will be performed to create 1000 imputed datasets. The following pseudo SAS code and seed (2438291) will be used for multiple imputation:

```

/*****
/* Note:
/* baseline = baseline lipid parameter
/* trtpn = treatment group: 0=placebo, 1=olezarsen 50 mg, 2=olezarsen 80 mg
/* stratt = baseline TG >= 500 mg/dL (5.65 mmol/L) Yes/No
*****/
proc mi data=adeff seed=2438291 nimpute=1000 out=adeff2;
    transform log(baseline) log(week5) log(week9) log(week13) log(week17) log(week21)
log(month6) log(week29) log(week37) log(week45) log(month12);
    mcmc;
    var stratt baseline week5 week9 week13 week17 week21 month6 week29 week37 week45
month12;
    by trtpn;
run;

```

The Step 2, 3 and 4 similar to that for TG imputation with an additional factor of baseline TG stratification factor will be used to create 100 imputation datasets.

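### For lipids other than TG, a missing baseline is imputed without the patient's own later values, which shifts that patient's expected percent change upward and adds avoidable noise

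*Combined protocol and SAP*

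**What the plan says.** SAP 4.2.2 averages the Day 1 pre-dose and Qualification values to obtain the baseline lipid, and falls back on Screening if all of those are missing. For lipids other than TG, a baseline that is still missing goes to the two-stage imputation in SAP 4.9.1.4, used "if baseline is missing for at least one randomized patient for given lipid parameter".

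- **Stage 1:** "First, the missing baseline fasting lipid value will be multiply imputed based on the observed baseline assessments from other patients". "The imputation model will include baseline fasting lipid value and baseline stratification factor", the factor being TG at or above 500 mg/dL, yes or no. The code agrees with the text: "var stratt baseline", with no post-baseline visit and no BY statement for treatment.
- **Hand-over:** "The imputed baseline values will be merged with the observed post baseline data and used for the second stage of imputation".
- **Stage 2**, by arm, models "baseline fasting lipid value, fasting lipid value at each post-baseline visits and baseline stratification factor". Its code lists "var baseline stratt week5 week9 week13 week17 week21 month6 week29 week37 week45" and Month 12, with one imputation for each stage 1 draw.
- **Lipids with no missing baseline** get a single PROC MI call with 1,000 imputations, by treatment group: "var stratt baseline week5 week9 week13 week17 week21 month6 week29 week37 week45" and Month 12.

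Under SAP 4.9.3.3, percent change is the dependent variable and log baseline is the covariate. The hierarchy in SAP 4.9.1.5 contains 9 lipids × 2 doses × 2 time points = 36 such comparisons.

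**The concern.** PROC MI fills only missing cells. Once stage 1 has filled the baseline, stage 2 takes it as data, so the patient's ten post-baseline columns never inform it. Given the TG stratum, the drawn baseline is unrelated to that patient's follow-up, yet it becomes both the denominator of percent change and the ANCOVA covariate. An imputation model that leaves out variables strongly related to the missing one breaks their correlation. When the imputed value is a denominator, this also biases the mean ratio. The unrelated draws also enter the stage 2 covariance as if observed, which weakens the baseline-to-visit relation used to fill Months 6 and 12.

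At stake is the accuracy of percent change for an affected lipid, in an analysis that the SAP writes specifically for this case.

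**Working it through.** **Inputs.** The documents give no log-scale SD, within-patient correlation or missing-baseline rate for any of these lipids, so there is no stated figure to reproduce. Assumed: s from 0.25 to 0.6, rho from 0.4 to 0.8, both within stratum. Arm sizes come from the 152 planned patients, split 1:1 and then 3:1: 76 per cohort, so 57 olezarsen per dose and 19 + 19 = 38 pooled placebo. The illustrative 60% reduction with no placebo change is the planning value for TG (SAP 4.12), borrowed as an assumption.

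**Step 1: bias for an affected patient.** Let baseline B and follow-up Y be lognormal with common log-SD s, correlation rho and median ratio R.

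- True mean ratio: E[Y/B] = R × exp(s²(1 − rho)).
- With a stage 1 draw B' unrelated to Y: E[Y/B'] = R × exp(s²).
- Inflation factor: exp(rho × s²), which exceeds 1 whenever rho is positive.

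Example with R = 0.5, s = 0.5: the true mean change is 0.5 × exp(0.10) − 1 = −44.7% at rho 0.6 and 0.5 × exp(0.05) − 1 = −47.4% at rho 0.8. Stage 1 gives 0.5 × exp(0.25) − 1 = −35.8% in both cases.

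| s, rho | Factor | True −60% becomes | True 0% becomes | True +30% becomes | A −60 point contrast becomes |
|---|---|---|---|---|---|
| 0.25, 0.4 | 1.03 | −59.0% | +2.5% | +33.3% | −61.5 |
| 0.4, 0.6 | 1.10 | −56.0% | +10.1% | +43.1% | −66.0 |
| 0.6, 0.8 | 1.33 | −46.6% | +33.4% | +73.4% | −80.0 |

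Both arms are multiplied by the same factor, so the difference between affected olezarsen and placebo patients widens.

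**Step 2: effect on the whole comparison, by hand.** With one missing baseline per arm at s = 0.4, rho = 0.6, the placebo mean rises by 10.1/38 = 0.27 points and the olezarsen mean by 4.0/57 = 0.07, a net 0.20 points away from zero. With a fraction p missing in every arm, the shift is about p × 60 × (factor − 1).

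**Step 3: simulation.** 400 trials per setting, arms 38/57/57, ten post-baseline columns, 20 imputations, ANCOVA with log baseline and stratum. Simplifications: complete follow-up and equal variances. The estimated difference in points, for a true reduction of 60%:

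| s, rho | Missing baselines | Full data | SAP stage 1 | Joint model by arm |
|---|---|---|---|---|
| 0.25, 0.6 | 10% | −60.22 | −60.46 | −60.36 |
| 0.4, 0.6 | one per arm | −60.42 | −60.60 | −60.47 |
| 0.4, 0.8 | 5% | −60.19 | −60.62 | −60.31 |
| 0.4, 0.8 | 10% | −60.21 | −61.22 | −60.39 |
| 0.6, 0.7 | one per arm | −59.78 | −60.47 | −59.86 |
| 0.6, 0.7 | 5% | −59.93 | −60.96 | −60.16 |
| 0.6, 0.7 | 10% | −60.28 | −61.86 | −61.12 |

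The second row's shift of 0.18 agrees with the 0.20 found by hand. The last row's 1.58 compares with 0.10 × 60 × (exp(0.252) − 1) = 1.72. The corner s = 0.6, rho = 0.8 is not among the settings shown; the hand formula gives 0.10 × 60 × 0.334 = 2.0 points there.

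**Step 4: noise.** In these settings one olezarsen patient's imputed percent change has an SD across imputations of 10 to 34 points under stage 1 and 7 to 17 under the joint model. The ratio runs from 10.1/7.4 = 1.4 (s = 0.25, rho = 0.6) to 18.7/8.6 = 2.2 (s = 0.4, rho = 0.8). At s = 0.4, rho = 0.8 and 10% missing, the empirical standard error of the difference is 4.45 on full data, 5.25 under stage 1 and 4.59 under the joint model.

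**The case against.** **The step will seldom run.** The lipid panel is drawn at Run-in, Qualification and Day 1 (protocol Appendix A), local values stand in for missing central ones (SAP 4.2.3), and TG from the same panel must exist at Qualification (SAP 4.9.1.4). Only a failure of that analyte at every pre-dose draw triggers stage 1. This stands, and it keeps the point minor. It does not make the rule sound when it is triggered.

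**The size rests on assumptions.** This stands too. At s = 0.25 and rho = 0.4 a true −60% becomes only −59.0%. Pooling 100 imputations also averages out part of the single-draw noise in the estimate, though that noise remains in the between-imputation variance. A general claim of very large noise is not established.

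**The joint model is not free of error.** It fits 12 variables by arm, with about 38 placebo patients, whereas stage 1 pools all patients. At s = 0.4, rho = 0.8 and 5% missing, affected placebo patients average +2.5% under the joint model against −0.5% on full data; stage 1 gives +13.1%. In the hardest setting (s = 0.6, rho = 0.7, 10% missing) the joint model is still off by 61.12 − 60.28 = 0.84 points, about half the stage 1 error of 1.58. It is better, not perfect.

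**Stronger readings to avoid.** A reader might infer that stage 1 dilutes the treatment effect because olezarsen reductions come out too small. The tested quantity is the difference from placebo, and placebo changes are inflated by more points, so in the assumed −60% settings the difference moves away from zero. A reader might also infer that one missing baseline spoils all nine lipids. The rule works lipid by lipid, so a missing apoC-III baseline affects apoC-III only.

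**Conclusion.** The point holds as a minor defect. Text and code agree that stage 1 ignores the patient's own post-baseline values, and nothing later in the SAP corrects it. The direction of the mean bias follows from the method under a lognormal model with positive within-patient correlation: upward for affected patients on average, though a single patient's draw can err either way. The size rests on assumed SDs and correlations. Across them the factor is 1.03 to 1.33. In the simulated −60% settings, imputation noise is about 1.4 to 2.2 times that of the joint model, and the bias in the olezarsen-placebo difference is about 0.1 to 0.7 points with one missing baseline per arm and up to about 1.6 points at 10% missing. These shifts are small beside a 60-point effect. The primary endpoint and all other TG endpoints are untouched, because SAP 4.9.1.4 states that baseline TG cannot be missing.

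**What to change.** Delete stage 1. Leave a missing baseline missing, and use for all nine lipids the single PROC MI call that the SAP now reserves for lipids with no missing baseline: 1,000 imputations, by `trtpn`, with `stratt`, `baseline`, every visit and Month 12 in the VAR list. Baseline and follow-up are then imputed together from the patient's own data. Steps 2 to 4 can follow as planned, since Step 3 discards only imputed values after the last observed one. The SAP gives code for the washout route only, so add a sentence saying that baseline is imputed in the same way if the retrieved-dropout route is used.

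The cost is small: one code path replaces two. The price is that baseline is estimated within arm, from a larger model and about 38 placebo patients; the SAP already relies on that model for post-baseline values. It would also help to report, per lipid and arm, how many baselines were imputed.
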